
1. INTRODUCTION AND RATIONALE

1.1 Introduction and problem description

Differentiated thyroid carcinoma (DTC) is rare (incidence: ~13-31/million patient years [1]). Although the prognosis is favourable, its morbidity is high. As most patient present with a palpable thyroid nodule (TN), with a lifetime prevalence of 3-8%, and the chance of cancer in any such a nodule is less than 5%, screening for cancer is warranted once a nodule is established. The prevalence of TNs increases with age. Nowadays, due to the increasing use of ultrasound (US) and other imaging techniques more and more asymptomatic TNs are discovered, the majority of which have no clinical relevance. As initial instrument, (US guided) fine-needle aspiration cytology (FNAC) is recommended. Aspirates are classified in six diagnostic categories according to the Bethesda System for Reporting Thyroid Cytopathology (Appendix III: The Bethesda System for Reporting Thyroid Cytopathology, §15.3, p91) [2, 3]. In about 75% of patients, this will lead to a definite diagnosis and treatment: either benign (Bethesda category II), suspicious (V) or definite malignant (VI). However in the remaining cases, repetitive FNAC cannot determine whether the lesion is benign or malignant, due to cellular atypia (III), follicular neoplasia (V) or repetitive nondiagnostic or unsatisfactory specimens (I). According to current practice, in all these patients diagnostic surgery is performed to reach a final histological diagnosis [4-6]. In about 69-88% these patients, the nodule is benign, and surgery was therefore futile. Especially in case the nodule was asymptomatic, the surgery was unbeneficial. Apart from symptoms and cosmetic complaints of the neck scar, about up to one third of these patients need lifelong daily thyroid hormone suppletion. Furthermore, although rare, surgical complications may be severe (haemorrhage, infection, permanent hoarseness) [7-9]. Finally, surgery, hospitalisation and sick-leave are costly. In most malignant thyroid nodules (~20-25% of operated patients), secondary surgery with adjuvant treatment including radio-active I-131 thyroid remnant ablation, has to be performed. Only in case of subcentimetre, indolent, unifocal papillary microcarcinoma (UPM), additional treatment is unnecessary.

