2.2 Secondary Objectives

2.2.1 Secondary Objective 1: Treatment Outcome

- SO1a: To determine the difference in unbeneficial treatment between FDG-PET/CT driven and routine surgery in this population including thyroid lesions of all sizes (i.e. both ≤10 mm and >10mm).
- SO1b: To determine the effect of incorporation of FDG-PET/CT on the complication-ratio.
- SO1c: To determine the false-negative rate of FDG-PET/CT in this population (i.e. in how many patients with malignancy will watchful-waiting be performed) based on both 12-month and (retrospective) 5-year follow-up.
- SO1d: To determine the influence of lesion size, pathological classification and patient characteristics on the diagnostic accuracy (subgroup analysis) of FDG-PET/CT.
- SO1e: To determine whether incorporation of FDG-PET/CT of the head and neck leads to overdiagnosis in non-thyroidal incidental findings (whole-group analysis).
- SO1f: To determine the short-term overall and disease free survival in both study arms.
- SO1g: To determine which factors hamper implementation of this modality for this indication (structured interviews).
- SO1h: To determine the fraction of patients that cannot be reassured by a negative PETscan (experimental arm only) despite careful selection of patients (implementability).

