4.2 Inclusion criteria

In order to be eligible for participation, a subject must meet ALL of the following criteria:

- Documented history of a solitary thyroid nodule or a dominant nodule within multinodular disease, with (*US-guided*) FNAC performed by a dedicated radiologist or experienced endocrinologist or pathologist, demonstrating an indeterminate cytological examination (i.e. Bethesda category III or IV, §15.3, p91) according to the local pathologist and confirmed after central review (§8.2.1, p46);
 - If a core needle biopsy was performed instead of a FNAC, the patient is eligible if the biopsy procedure was felt to be minimally disruptive to the nodule architecture, based on a review by the principal investigator or nuclear medicine investigator.
- Scheduled for surgical excision (preferably) within 2 months of the inclusion date;
- Age \geq 18 years;
 - This disease is rare in children and therefore the study will be limited to adults.
- Euthyroid state with a serum TSH or a free T4 level within the institutional upper and lower limits of normal, measured within 2 months of registration. In case of a suppressed TSH: a negative ¹²³I, ¹³¹I or ^{99m}TcO₄⁻ scintigraphy must be available ("cold nodule");
 - Mild deviations from the institutional normal limits may be considered acceptable if the patient has achieved a clinically euthyroid state with medication at a stable dose for >3 months, and the TSH is considered to be at target by the patient's treating physician. In patients with hyperthyroidism requiring treatment, this euthyroid state may be achieved with administration of a thionamide prior to FDG-PET/CT exam.
 - Patients with active (according to treating physician) hyperthyroid inflammatory conditions such as thyroiditis (e.g. m. Graves, Hashimoto, deQuervain, etc.) and toxic multinodular goitre often exhibit increased glucose uptake resulting in diffuse uptake of FDG which may obscure visualization of a thyroid tumour. These patients are not eligible for participation due to an expected higher false-negative rate.
- In patients with multinodular disease and a dominant nodule, the nuclear medicine physician responsible for FDG-PET/CT scan interpretation must determine whether the nodule is likely to be discriminated on FDG-PET/CT imaging prior to enrolment;
- Willing to participate in all aspects of the study;

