8.1.2 Secondary study parameters/endpoints

Secondary treatment outcome parameters (SO1, §2.2.1, p30):

- Complication fraction
 - Complications include: bleeding (requiring intervention or prolonging admission), infection (requiring intervention or prolonging admission), re-operation, ICUadmission, (temporary) hoarseness, (temporary) thyroid hormone suppletion or calcium/vitamin D suppletion.
- FDG-PET/CT diagnostic accuracy,
 - True-positive
 - True-negative
 - o False-positive
 - o False-negative
- Fraction of extra diagnostics due to coincidental FDG-PET/CT-findings,
- (Overall Survival and Disease Free Survival determined when last study-related followup of last included patient has been completed),
- Description of factors hampering implementation,
- As this study is performed intention-to-treat: the fraction and reasons of patients in the experimental study arm that still want a hemithyroidectomy despite a negative FDG-PET/CT scan.

Secondary HRQoL outcome parameters (SO2, §2.2.2, p30):

- Personal assessment in all domains of the EQ-5D-5L, the RAND-36 v2.0 (validated translation of the SF36-II), the ThyPRO and the Distress Thermometer (without the problem list) (including temporal relation),
- From the utility (EQ-5D-5L index) and overall survival, the number of QALYs are determined.

Secondary costs and cost-effectiveness parameters (SO3, §2.2.3, p31):

- Volumes of care including hospitalization days,
- iNMB (using QALYs saved as effect) including sensitivity analysis,
- iNMB (using unbeneficial treatment prevented as effect),
- Results of the iPCQ and iMCQ domains, including sick leave days.

Secondary tissue (nodule) parameters (SO4, §2.2.4, p31):

Performed on all (benign and malignant) resected lesions:

- US features (size, border, halo, calcifications, etc.)
- FDG-PET/CT features (SUV_{max}, SUV_{peak}, SUV_{mean}, metabolic volume, TLG)
- Cytological morphological features (Bethesda criteria, atypia, etc.)
- Histological morphological features (diagnosis, invasiveness, stage, atypia, etc.)
- Cytological and histological immunohistochemical features ((semi)quantitative: e.g. GLUT, HK, CA-IX, HIF-1α, Ki67/MIB, caspase-3, galectin-3, Tg, CD3, CD31/34)
- Cytological (tumour)genetic features and biomarkers: genetic profiling for gene alterations (mutations, fusions, rearrangements), gene expression, miRNA expression, and copy-number variations using next-generation sequencing and/or multigene classifier.

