The cost-analysis exists of two main parts. First, on patient level, volumes of care will be measured prospectively using questionnaires filled-in by patients, completed by case record forms and patient files (supported by patient-based diaries). Per study-arm (experimental and control) full cost prices will be determined using activity-based costing (obviously) excluding the costs of the FDG-PET/CT in the control study arm. Cost items included are e.g.: surgical costs, costs of ¹³¹I-RIA, admission costs, costs for complications (secondary surgery, ICU etc.), out-patient clinic visits, use of relevant medications (calcium, vitamin D, 69iothyronine69, 69iothyronine etc.), blood tests ((para)thyroid function tests) and additional investigations (US, CT, biopsy, histopathology, etc.). Productivity losses for patients (sick leave) will be estimated using the iPCQ. The friction cost-method will be applied following the Dutch guidelines [68]. Also travel time to an out-patient clinic and related expenses will be considered using the iMCQ. The second part of the cost-analysis consists of determining the cost prices for each volume of consumption in order to use these for multiplying the volumes registered for each participating patient. The Dutch guidelines for cost-analysis will be used [68]. For units of care/resources where no guideline of standard prices is available, real cost prices will be determined.

Patient outcome analysis:

The effect analysis adheres to the design of a randomised controlled trial and measures at baseline (T0) and after surgery+¹³¹I-RIA/2 months, 6 months and 12 months (T1-3) follow-up. To measure the quality of the health status of the patients, a validated HRQoL instrument will be used: the EQ-5D-5L. This HRQoL instrument will be completed by the patients and is available in a validated Dutch translation [70]. The EQ-5D-5L is a generic HRQoL instrument comprising five domains: mobility self-care, usual activities, pain/discomfort and anxiety/depression. The EQ-5D-5L index is obtained by applying predetermined weights to five domains. This index gives a societal-based global quantification of the patients' health status on a scale ranging from 0 (death) to 1 (perfect health). Patients will also be asked to rate their overall HRQoL on a visual analogue scale (EQ-5D-VAS) consisting of a vertical line ranging from 0 (worst imaginable health status) to 100 (best imaginable).

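### The complication endpoint does not separate planned completion surgery for cancer, and the hormone replacement that follows it, from complications, so the complication ratio for objective SO1b is pulled towards 1

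*Protocol*

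**What the plan says.** Secondary objective SO1b (section 2.2.1) is "To determine the effect of incorporation of FDG-PET/CT on the complication-ratio". Section 8.1.2 gives the endpoint as a complication fraction and lists what it includes. Two items are limited: "bleeding (requiring intervention or prolonging admission), infection (requiring intervention or prolonging admission". The rest are not: "re-operation, ICUadmission, (temporary) hoarseness, (temporary) thyroid hormone suppletion or calcium/vitamin D suppletion".

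Three other places bear on how the open items would be scored:

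- Section 1.1 says that in most malignant nodules (about 20-25% of operated patients) "secondary surgery with adjuvant treatment including radio-active I-131 thyroid remnant ablation, has to be performed". It exempts subcentimetre unifocal papillary microcarcinoma.
- Section 10.6 names, as a cost item, "costs for complications (secondary surgery, ICU etc".
- Section 1.1 also says that after diagnostic surgery for a benign nodule "about up to one third of these patients need lifelong daily thyroid hormone suppletion".

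No passage takes planned completion thyroidectomy, or the hormone replacement that follows it, out of the complication fraction.

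**The concern.** Completion thyroidectomy after a diagnostic hemithyroidectomy is literally a re-operation, and the hormone replacement that follows is literally hormone suppletion. If both are scored as listed, most correctly diagnosed and treated cancers become complications by definition.

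FDG-PET/CT can lower surgical harm mainly by sparing operations in PET-negative patients. Intended cancer treatment is expected to occur at nearly the same rate in both arms. Mixing it into the endpoint adds a large, almost constant amount to each arm, so the ratio moves towards 1 and no longer describes surgical harm. At stake is the reading of SO1b, and of the complication costs in section 10.6 if they use the same classification.

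**Working it through.** **Inputs from the protocol.** Pooled counts (Appendix IV, consistent with section 1.3): 55 true positive, 87 false positive, 80 true negative, 3 false negative, total 225. Arm sizes (section 4.4): 88 in arm A, 44 in control.

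**Check of the counts against the protocol's own figures.** Surgeries cancelled in arm A: 88 × 83/225 = 32.5, against about 32 in section 3. False negatives: 3/225 = 1.3% of all patients and 3/83 = 3.6% of negative scans, both as stated in section 8.8. The protocol gives no expected rate or power for the complication endpoint itself.

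**Step 1: how many patients could be affected.** In control all cancers are operated on. In arm A only PET-positive cancers are.

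- Control: 58/225 = 25.8%, or 44 × 58/225 = 11.3 patients.
- Arm A: 55/225 = 24.4%, or 88 × 55/225 = 21.5 patients.

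For planned second operations these are upper bounds. Section 1.1 says most, not all, and exempts unifocal microcarcinoma. Sections 8.3.1 and 8.3.4 allow an initial total thyroidectomy, which needs no second operation.

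**Step 2: effect on the ratio.** Assumptions: every operated patient has genuine complication risk c; a fraction f of operated cancers has planned completion treatment; the two are independent. The chance that an operated cancer has at least one counted event is a = 1 − (1 − c)(1 − f). Then

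- control = (58a + 167c)/225
- arm A = (55a + 87c)/225

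| c | f | Control | Arm A | Ratio A/control |
|---|---|---|---|---|
| 0.05 | 0.8 | 24.6% | 21.7% | 0.884 |
| 0.10 | 0.8 | 28.6% | 23.9% | 0.837 |
| 0.20 | 0.8 | 36.5% | 28.3% | 0.774 |
| 0.33 | 0.8 | 46.8% | 33.9% | 0.725 |
| 0.05 | 1.0 | 29.5% | 26.4% | 0.894 |
| 0.10 | 1.0 | 33.2% | 28.3% | 0.853 |
| 0.33 | 1.0 | 50.3% | 37.2% | 0.740 |

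Example, c = 0.10 and f = 0.8: a = 1 − 0.9 × 0.2 = 0.82. Control = (58 × 0.82 + 167 × 0.10)/225 = 64.26/225 = 28.6%. Arm A = (55 × 0.82 + 87 × 0.10)/225 = 53.80/225 = 23.9%. The only protocol figure near c is the upper value of about one third for hormone need in section 1.1. The lower values of c, and both values of f, are assumptions.

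**Step 3: the ratio with planned cancer treatment removed.** Let genuine risk in treated cancers be k times c, since a second operation may bring complications of its own. The ratio is (87 + 55k)/(167 + 58k):

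- k = 1: 142/225 = 0.631
- k = 2: 197/283 = 0.696
- k = 3: 252/341 = 0.739

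**Step 4: does the direction survive k above 1?** Use the same k on both sides, so a = 1 − (1 − kc)(1 − f), with c = 0.10 and f = 0.8.

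- k = 2: a = 1 − 0.8 × 0.2 = 0.84. As written (55 × 0.84 + 8.7)/(58 × 0.84 + 16.7) = 54.90/65.42 = 0.839, against 0.696.
- k = 3: a = 1 − 0.7 × 0.2 = 0.86. As written 56.00/66.58 = 0.841, against 0.739.

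The added events stand in the ratio 55/58 = 0.948 between the arms, above each restricted ratio in step 3, so adding them raises the ratio. The gap closes when genuine risk in treated cancers is already near 100%. At c = 0.33 and k = 3, kc = 0.99 and a = 1 − 0.01 × 0.2 = 0.998, giving (54.89 + 28.71)/(57.88 + 55.11) = 0.740, against 0.739.

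**The case against.** The strongest reply is that the governing word is complication, and planned treatment is not one. Elsewhere the protocol keeps the two apart: Table 2 places therapeutic surgery with radioiodine under treatment, and section 1.4.1 prices completion thyroidectomy separately from permanent complications. Event coding could also be settled in a SAP or case report form that is not shown.

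This does not settle the matter. The list already counts hormone use, which section 1.1 presents as a common sequel of the operation, so ordinary meaning does not mark the boundary. Section 10.6 points the other way by naming secondary surgery as a complication cost. The list is also fixed in the protocol, with conditions on two items and none on these.

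Three stronger readings may tempt a reader, and the protocol does not support them:

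- *A missed cancer is credited to PET as a complication avoided.* About 88 × 3/225 = 1.2 such patients are expected in arm A. A patient who is not operated on within the 12-month window has had no surgical complication, and would still score as complication-free under a tighter definition. The harm of a missed cancer is counted in the primary endpoint (section 8.1.1) and in SO1c.
- *Medication used at entry scores as a complication.* Section 4.2 admits patients in a "clinically euthyroid state with medication at a stable dose for >3 months", but the only drug class it names is a thionamide, which is not hormone suppletion. Section 8.1.3 records medication, and no frequency is given. Wording that requires a new start is a small clarification only.
- *The ratio should be 0.63.* That needs k = 1, meaning no extra genuine risk from cancer surgery. Step 3 shows 0.70 to 0.74 at k = 2 to 3.

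**Conclusion.** The point stands for completion surgery and the hormone replacement that follows it. Read as written, section 8.1.2 together with section 10.6 lets intended cancer treatment count as a complication in up to 25.8% of control patients and 24.4% of arm A patients. Under the stated model this moves the SO1b ratio towards 1, which works against PET rather than for it.

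The size is not fixed by the protocol. With 80% of operated cancers completed and equal genuine risk in all operated patients, the as-written ratio is 0.725 at 33% risk and 0.884 at 5% risk. The dilution is mildest where genuine risk is high, as it may be if hormone use after benign surgery approaches the upper figure in section 1.1. No single undistorted value can be stated, because genuine complications of completion surgery belong in the endpoint.

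SO1b is a secondary objective with no stated power. The primary endpoint and the sample size do not depend on this definition.

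**What to change.** In section 8.1.2:

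- replace re-operation with unplanned re-operation for a complication;
- replace the supplementation items with thyroid hormone or calcium/vitamin D supplementation newly started after surgery;
- state that completion thyroidectomy for malignancy, and thyroid hormone replacement after total or completion thyroidectomy for malignancy, are not counted but are reported separately by arm as cancer treatment;
- state that genuine complications of completion surgery still count.

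Align section 10.6 so that secondary surgery is costed as a complication only when it is unplanned and done for one, with completion surgery costed as treatment. Settle the wording before the arms are compared.

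The cost is wording. Histology (section 8.1.2), medication (section 8.1.3) and surgical reports (section 12.1) are already collected, and no patient's management changes. The one downside is that the stated complication fraction will be lower in both arms, so it will not compare directly with any figure that uses the broader definition.

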3. STUDY DESIGN

A partially-blinded, prospective, multi-centre, block-randomised controlled trial (RCT) is designed. After obtaining written informed consent, patients are registered centrally, FNAC is reviewed centrally and thereafter patients are randomised to either the experimental study-arm (arm A: FDG-PET/CT driven management decisions) or a control study-arm (arm B: surgery regardless FDG-PET/CT result) using a 2:1 allocation ratio. The latter is performed both for methodological purposes (the treatment of the subjects in the control study arm is well investigated and described before) and to satisfy the assumption that patient prefer the experimental study-arm. The result of randomization is blinded to the treating physicians and central FDG-PET/CT review committee. Allocation is adaptively stratified using the minimisation method on the centre of inclusion and the most prognostic features of DTC known at this stage of patient work-up: (US) lesion size (0-10 mm/11-20 mm/21-40 mm/40+ mm), patient sex, patient age (<45yr, \geq 45yr) and Bethesda classification according to central review committee (atypia of unknown significance/follicular lesion of unknown significance (III) or (suspicion) for a follicular neoplasia (IV)).

Based on the study arm allocation and PET result, treating physicians will either be told to cancel scheduled diagnostic thyroid surgery (allocation to the experimental arm with a negative FDG-PET/CT at central review or ~32/132 patients) or to proceed with surgery (all other cases or 100/132 patients). In case surgery is cancelled the patients need to be followed-up by watchful waiting and a confirmatory ultrasonography (including FNAC) after 12 months. Patient allocation will not be disclosed to prevent study withdrawal, however in case surgery is cancelled unblinding is unavoidable (~25% of all included patients).

The Gold Standard is histology, revised by a (central) dedicated pathologist panel, obtained from surgery or 12-months follow-up, including US (+FNAC). All patients will be followed for at least 12 months after FDG-PET/CT to ensure all direct costs and complications are noted. Five years after inclusion of the last patient, long-term follow-up will be determined based on patient file review and contact with the general practitioner (flowchart Figure 1, p34 and

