4.4 Sample size calculation

Based on the main objective, it is expected that FDG-PET/CT can reduce unjust treatment from ~73.1% (=136/186 benign lesions >10mm) to ~40.3% (=75/186 false-positive and false-negative lesions >10mm, §1.3, p19). Using G*Power version 3.1.9.2. (and validated using JMP from SAS version 9.0.1, STATA version 12.0SE and PASS version 2011), we computed using an α error probability of 0.025 (=0.05/2, Bonferroni correction for interim analysis) a power of 0.80 and an allocation ratio of N_A:N_B=2:1, we need to include at least 90 patients in total (one-tailed test) to establish this difference (60+30 patients in arm A and B respectively).

Since around 82.7% (=186/225, §1.3, p19) fulfil the size criterion, at least 111 patients (74+37 patients in arm A and B respectively) need to be included. Accounting for additional 15% data loss at the final end-point, 132 patients should be included (88+44 patients in arm A and B respectively) (Figure 2, p40).

This total number of patients could at best (assuming no data loss) discern a reduction of 26.6% unjust treatment in the whole population with an actual α error probability of 0.016 and a power of 0.80. This is based on a reduction from 74.2% (prevalence of benign disease in all 225 patients) to 47.6%. In the experimental arm (88 patients), where the number of false-negative PET is estimated to be ~1.3% (3/225), this number of patients should establish a false-negative rate of maximal 7.5% (actual α error probability of 0.0066 and a power of 0.80). All analyses will be performed according to the intention-to-treat principle, meaning that analysis is based on the initial study-arm allocation and not on the treatment eventually received (e.g. a FDG-PET/CT negative patient in the experimental arm does not refrain from surgery and therefore actually is treated according to the control study arm).

[figure not shown]

Figure 2: Relation between study size (N), study-arm size sizes (n₁ and n₂) and effect size. Empirical relation: N=16.33935*ES^{-1.86986}, R²=.999443). Expected ES=73.1%-40.3%=32.8%

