5.1 Investigational product/treatment

An FDG-PET/CT is a widely available, routinely used diagnostic modality. As elaborated further in §8.3.1, p48, it requires limited preparation, administration of FDG does not result in any adverse events and the risks resulting from the radiation dose (~5 mSv for a whole-body investigation, 3.3-3.5 mSv for an average weighted adult head/neck FDG-PET/LDCT) are limited (see §15.6: Appendix VI: Radiation Ethics Form, p97). All involved centres have their own PET-CT/scanner.

All patients were scheduled for diagnostic thyroid surgery by an experienced surgeon prior to inclusion to this trial. In case of either a positive FDG-PET/CT in the experimental arm or inclusion in the control arm, scheduled surgery will be performed. In case of a negative FDG-PET/CT in the experimental arm, surgery will be cancelled and follow-up will be performed.

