8.3.5 Tissue genetic analysis

All cytology specimens will be genetically profiled using various molecular biomarkers. These tissue markers will include point mutations (e.g. BRAF and RAS point mutations), gene fusions and gene rearrangements (e.g. RET/PTC and PAX8/PPARγ rearrangements), gene and miRNA expression profiling, and copy-number variations, and possibly immunocyto- and immunohistochemical markers.

Testing techniques for molecular tissue biomarkers are rapidly developing globally. Nonetheless, as mentioned in a previous paragraph, these techniques are not yet available at Radboudumc (§1.10 Laboratory infrastructure and available techniques).

We will perform molecular diagnostics at the Leiden University Medical Centre (LUMC) (at the pathology lab of prof. dr. [name]) using state of the art next generation sequencing techniques and biomarker panels. For this purpose, cytology slides from all study participants will be sent to the LUMC. Informed consent was obtained from the study participants for these analyses.

Molecular testing on cytology requires the extraction of ± 20 ng of DNA/RNA from the existing cytology slides. To extract sufficient nucleotides, part of the cytological material will be scraped of one or two cytology slides from each patient. Prior to DNA/RNA extraction, all cytology slides

will be scanned and digitally stored; these images will be made available to and saved at the hospital where the FNA was performed, in order to enable any desired morphological review of cytology in the future. This method is also regularly used in a clinical setting. Destruction of (parts of) cytology slides disables any further staining, immunocytochemistry or other cytology testing in the future. However, as cytology review has already been completed at that point in the current study and the individual patient's treatment has been determined and executed (i.e. most patients will have undergone surgery), this will have no consequences for individual patient.

If appropriate, some cytology and histology samples may additionally be selected for further molecular testing at LUMC. This may e.g. concern Hürthle cell lesions and any copy number variations detected.

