 Table 7: Parameters describing association between variables.

Statistic:	Number		
Correlation Coefficient (R)	1	R=0?	t-test
		R=value	Fisher's z Transformation
	2	Independent	
		Dependent	
Regression Coefficients	1		t-test
	2		

 Table 8: Comparison between parameters describe association

Se, Sp, PPV and NPV will be computed using the traditional formulae, using the definition for true/false positive as described in Table 9, p67, §8.3, p48:

Sensitivity: $Se = \frac{TP}{TP+FN}$, $Specificity: Sp = \frac{TN}{TN+FP}$ Accuracy: $Acc = \frac{TP+TN}{TP+TN+FP+FN}$, $Prevalence: Prev = \frac{TP+FN}{TP+TN+FP+FN}$ Positive Predictive Value: $PPV = \frac{TP}{TP+FP}$, $Negative Predictive Value: NPV = \frac{TN}{TN+FN}$ Positive Likelihood Ratio: $LR + = \frac{Se}{1-Sp}$, $Negative Likelihood Ratio: LR - = \frac{1-Se}{Sp}$ Diagnostic Odds Ratio: $dOR = \frac{LR+}{LR-}$, $SE(LOG(dOR)) = \sqrt{\frac{1}{TP} + \frac{1}{TN} + \frac{1}{FP} + \frac{1}{FN}}$ [69]

	Disease +ve	Disease –ve
Test +ve	TP	FP
Test –ve	FN	TN

Table 9: Definition of true positive (TP), true negative (TN), false-positive (FP) and false-negative (FN).

Threshold effects of FDG-uptake in de nodules will be assessed using receiver-operating characteristic (ROC) curves and quantified using the area under the curve (AUC), as Se and Sp are inversely related. The standard error (and thus the 95%-CI) of the AUC can be computed either under a bi-negative exponential assumption (used only when the number of positive actual states is equal to the number of negative actual states) or using a non-parametric assumption (used in all other cases).

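### The SO4 tissue and FDG parameters are set on resected lesions, a set that by design keeps about one third of PET-negative nodules, and section 8.3.5 names a different set

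*Protocol*

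**What the plan says.** Section 8.1.2 heads the secondary tissue (nodule) parameters for SO4 with "Performed on all (benign and malignant) resected lesions". The list below that line covers ultrasound features, FDG uptake measures ("FDG-PET/CT features (SUV" and so on, with metabolic volume and TLG), cytological and histological morphology, immunohistochemistry, and cytological genetic markers.

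Who is resected is fixed elsewhere. Section 5.1 states: "In case of a negative FDG-PET/CT in the experimental arm, surgery will be cancelled and follow-up will be performed". Section 3 puts the cancelled group at "allocation to the experimental arm with a negative FDG-PET/CT at central review or ~32/132 patients", with the other 100 of 132 operated on, and describes a "control study-arm (arm B: surgery regardless FDG-PET/CT result) using a 2:1 allocation ratio".

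Other sections name a different set or none:
- Section 8.3.5 profiles all cytology specimens and says "cytology slides from all study participants will be sent to the LUMC". It then matches the profiles to histopathology, which unoperated patients lack. It also foresees genetic results in patients who were not operated on.
- Table 2 ticks tissue and genetic analysis for arm A without the PET-positive-only footnote that it attaches to arm A histopathology.
- Section 10.3 says "Threshold effects of FDG-uptake in de nodules will be assessed using receiver-operating characteristic (ROC) curves" and names no analysis set.

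SO4b (section 2.2.4) asks whether PET combined with molecular markers gives higher pre-operative accuracy, and whether markers relate to false PET results.

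**The concern.** In the resected set, inclusion depends on the test under study. PET-positive nodules enter from both arms and PET-negative nodules essentially from arm B only. True negatives and false negatives are therefore under-sampled about threefold relative to true and false positives, even though every lesion in the set has histology.

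SO4b needs PET's own sensitivity and specificity as the comparator for any PET-marker combination. If that comparator comes from the resected pool without correction, it does not describe the population for whom the test is meant. The same holds for correlations between markers and FDG uptake pooled over all resected lesions.

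The protocol already applies the right principle elsewhere. Its false-negative safety checks (sections 8.4.1 and 8.7) use the control arm only, and section 11.4 notes that this is the arm with both PET and final histology. Nothing carries that reasoning over to SO4, and no section weights the resected set.

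**Working it through.** **Inputs.** Appendix IV, pooled row: TP 55, FP 87, TN 80, FN 3 (N = 225). Section 4.4: "132 patients should be included (88+44 patients in arm A and B respectively").

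**Reproducing the plan's own figures.**
- PET-negative fraction = (80 + 3)/225 = 36.9%.
- Arm A PET-negative = 88 × 0.369 = 32.5, and operated = 132 − 32.5 = 99.5. These agree with the stated 32 and 100 of 132.
- Sensitivity 55/58 = 94.8%, specificity 80/167 = 47.9% and prevalence 58/225 = 25.8% also agree with Appendix IV.

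**Expected resected set.** PET-positive cells come from all 132 patients and PET-negative cells from the 44 in arm B:
- TP = 132 × 55/225 = 32.3
- FP = 132 × 87/225 = 51.0
- TN = 44 × 80/225 = 15.6
- FN = 44 × 3/225 = 0.6

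This keeps all 83.3 expected PET-positive nodules and 16.2 of 48.7 PET-negative ones.

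| Quantity | All nodules | Resected, unweighted |
|---|---|---|
| Sensitivity | 94.8% | 32.3/32.9 = 98.2% |
| Specificity | 47.9% | 15.6/66.7 = 23.5% |
| LR+ | 1.82 | 1.28 |
| Accuracy | 60.0% | 48.1% |
| Prevalence | 25.8% | 32.9/99.5 = 33.0% |
| PET-negative share | 36.9% | 16.2/99.5 = 16.3% |
| PPV | 38.7% | 38.7% |
| NPV | 96.4% | 96.4% |

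**Crossover.** The number of arm A PET-negative patients operated on anyway is not given. Assume a fraction c of them, independent of disease, and let f = 44 + 88c. Specificity is then 80f/(80f + 132 × 87), which is 23.5% at c = 0 and 30.0% at c = 0.20.

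**A marker's own specificity (assumed marker).** Let marker positivity in benign nodules be a if PET-positive and b if PET-negative, centred on 30%. Full-population specificity is [87(1 − a) + 80(1 − b)]/167. In the resected set the two groups are weighted 132 × 87 and 44 × 80.
- a = b: 0.700 in both sets, so no change.
- a and b 10 points apart: 0.698 becomes 0.673.
- a and b 40 points apart: 0.692 becomes 0.594.

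**SUV ROC, if run on this set.** Under an assumed equal-variance binormal model matched to the pooled sensitivity and specificity, simulation gives an AUC of about 0.87 in all nodules and 0.84 in the resected set.

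**Correction.** Arm B alone, or weight 132/44 = 3 on arm B PET-negative lesions, returns 94.8%, 47.9% and 25.8%. In expectation this follows from the construction. It shows that the weight matches the sampling and is not independent evidence.

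**The case against.** The strongest reply is that the protocol never prescribes a pooled, unweighted accuracy analysis of resected lesions. Section 8.1.2 may only say where parameters are measured, and the handling of an exploratory objective can be left to an analysis plan that is not shown here. Section 8.3.5 and Table 2 suggest that the heading in 8.1.2 is loose wording, and histological immunohistochemistry cannot avoid resected tissue in any case.

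Part of this stands. For the genetic markers the defect is a conflict between sections rather than a settled restriction. The bias arises only if the stated set is used without correction. But the protocol does state that set, for SUV features and cytological markers as well as for tissue that requires surgery. An analyst who follows it would obtain the biased quantities. That immunohistochemistry needs resected tissue makes arm B restriction or weighting more necessary for it.

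A reader might also infer several stronger things that the document does not support:
- **That the trial's PET accuracy endpoint is biased in this way.** PET diagnostic accuracy is listed under SO1, outside the restriction, and section 3 gives unoperated patients a 12-month reference of ultrasound with or without FNAC.
- **That the SUV ROC is fixed on resected lesions.** Section 10.3 names no set; the link exists only because SUV features are listed under SO4. The modelled AUC shift is also smaller than one standard error (about 0.045 by Hanley-McNeil with 33 malignant and 67 benign lesions).
- **That every SO4 result is distorted.** PET's PPV and NPV do not move. Nor do analyses within PET-positive or PET-negative nodules, which cover much of the question about markers of false PET results.
- **That an add-on marker will look more useful than it is.** No calculation here shows this. In the examples above, the marker's own specificity falls.

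**Conclusion.** The point holds in a limited form. The SO4 analysis set is contradictory between sections 8.1.2 and 8.3.5 with Table 2, and the set named in 8.1.2 is selected on the PET result by design.

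Used unweighted against histology, it would roughly halve the apparent specificity of the PET comparator and raise its sensitivity and the prevalence, by the amounts tabulated above. Combined PET-marker accuracy, pooled marker-FDG correlations, marker PPV and NPV (through prevalence), and any SUV ROC run on this set would shift as well. A marker's sensitivity and specificity change only if the marker is related to FDG uptake given disease, which is the relation SO4 sets out to study.

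The sizes assume that the Appendix IV pooled counts apply to this trial, that allocation is 88 to 44, and that arm A PET-negative patients are not resected. Disease-independent crossover of up to 20% leaves specificity at 30.0% or below. The AUC and marker figures rest on assumed models and only illustrate direction and rough size. The primary endpoint is not involved.

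**What to change.** 1. Reconcile sections 8.1.2 and 8.3.5 with Table 2, and name the analysis set for each SO4 parameter. Describe cytology and PET features in all participants, and limit only the histology-based parameters to resected tissue.
2. For sensitivity, specificity, likelihood ratios, ROC curves, marker-FDG correlations and combined-test accuracy against histology, specify one of two sets:
   - arm B alone; or
   - all PET-positive resected lesions plus arm B PET-negative lesions, the latter weighted by the inverse of the achieved control-arm fraction among PET-negatives (about 3).
3. Leave arm A PET-negative patients who are operated on outside the allocation rule out of the weighted set, and describe them separately. Section 10.1 foresees such surgery for high clinical suspicion, so these lesions may be selected on disease.
4. State the set for the SUV ROC in section 10.3.

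The cost is wording and a weighted analysis of data already collected. The price is precision: only about 16 arm B PET-negative lesions, with about 0.6 expected false negatives, carry the PET-negative information. Intervals will be wide, and statements about markers of false-negative PET will be weak under either option.
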